#### 8.3.1.2. Analysis of the change in TS-PGII

The change in the TS-PGII score from baseline to week 12 (2nd secondary endpoint) will be analyzed using a Cochran-Mantel-Haenszel (CMH) row mean score test with modified ridit scoring, controlling for baseline TS-PGII. The TS-PGII will be summarized as shifts from baseline score to each visit that it is measured using descriptive statistics.

The SAS code for the analysis at week 12 is as follows:

A large rectangular area of the page has been completely blacked out, obscuring several lines of SAS code. The redaction is irregular, with jagged edges and varying shades of black.

### 8.3.2. Sensitivity Analysis

A large rectangular area of the page has been completely blacked out, obscuring several lines of SAS code. The redaction is irregular, with jagged edges and varying shades of black.

Figure 1 consists of three horizontal bar charts. The top chart has three bars: the first is black, the second is white, and the third is black. The middle chart has three bars: the first is black, the second is white, and the third is black. The bottom chart has three bars: the first is black, the second is white, and the third is black. All bars are of equal length.

## 8.4. EXPLORATORY ENDPOINTS AND ANALYSIS

Term	Percentage
GMOs	85%
Organic	82%
Natural	78%
Artificial	75%
GMOs	80%
Organic	75%
Natural	72%
Artificial	68%
GMOs	88%
Organic	85%
Natural	82%
Artificial	78%
GMOs	80%
Organic	78%
Natural	75%
Artificial	72%
GMOs	82%
Organic	75%
Natural	70%
Artificial	65%

A series of black horizontal bars of varying lengths, likely representing data in a redacted table. The bars are arranged vertically and are set against a white background. The lengths of the bars correspond to the values in the table, with the longest bar representing the highest value and the shortest bar representing the lowest value. The bars are positioned in a way that suggests they are part of a larger table that has been redacted for security reasons.

## 9. SAFETY

The safety endpoints for this study are as follows:

- Incidence of adverse events
- Observed values and changes from baseline in vital signs
- Observed values and change from baseline in the Children's Depression Inventory, Second Edition (CDI-2), Parent and Self-report Profiles
- Observed values in the Children's Columbia-Suicide Severity Rating Scale (C-SSRS)
- Observed values in electrocardiogram (ECG) parameters and shifts from screening for clinically significant abnormal findings
- Observed values and changes from screening in clinical laboratory parameters (hematology, chemistry, and urinalysis)

The safety analysis set will be used for all safety analyses. Summaries will be presented by treatment group and for all patients.

### 9.1. EXTENT OF EXPOSURE

Duration of exposure to study drug (days) for individual patients is the number of days patient received drug (last day of study drug – first day of study drug + 1). Duration of treatment (days) will be summarized using descriptive statistics. Weeks on treatment using the categories  $\leq 2$  weeks,  $>2$  to  $\leq 4$  weeks,  $>4$  to  $\leq 6$  weeks,  $>6$  to  $\leq 9$  weeks,  $>9$  to  $\leq 12$  and  $>12$  weeks will also be summarized using descriptive statistics.

Also, the actual daily dose during each week in maintenance period will be summarized by treatment, age group, weight group, and CYP2D6 status. Furthermore, the frequency and percentage of patients reached the maximum daily dose allowed will be provided. Bar plot of patients reached the maximum daily dose will be presented. A Kaplan-Meier Curve will be used to present the time to the maximal dose in days by treatment, age group, weight group, and CYP2D6 status.

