3.11. Stopping Rules and Discontinuation Criteria

There are no formal rules for early termination of this study. During the conduct of the study, serious adverse events will be reviewed (see Section [7.1.5](#)) as they are reported from the investigational center to identify safety concerns. The study may be terminated by the sponsor at any time.

A patient may discontinue participation in the study at any time for any reason (eg, lack of efficacy, consent withdrawn, and adverse event). The investigator and/or sponsor can withdraw a

patient from the study at any time for any reason (eg, protocol violation or deviation as defined in Section 11.1.2, noncompliance, or adverse event).

Please see Section 4.4 for the withdrawal criteria and procedures.

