5. TREATMENT OF PATIENTS

5.1. Drugs Administered During the Study

IMP (see Section 3.8) will be administered as oral tablets at a starting dose of 6 mg. Titration schemes based on body weight at baseline are shown in [Table 2](#). The maximum daily dose is determined by body weight and CYP2D6 impairment status at baseline. Although dose adjustments can be made up to and including the week 7 telephone call, if a stable dose is reached before then, the patient should continue taking that dose for the remainder of the titration period and throughout maintenance dosing. If a patient experiences a “clinically significant” adverse event that is attributed to the IMP, the investigator will determine if a dose reduction or suspension is necessary. At the end of the titration period, the patient’s dose will be established for the maintenance period. If a patient experiences an adverse event during the maintenance period and the investigator believes a dose reduction is warranted, the dose may be reduced.

IMP will be dispensed in the clinic. Patients will receive doses for 2 weeks at baseline, week 2, and week 4 visits (current dose level and next dose level) to cover the telephone contacts. At week 6 and week 9 visits, patients will receive doses for 3 weeks.

IMP will be administered as follows:

- IMP should be swallowed whole and taken with food. Tablets should be taken with food (eg, a snack) and should not be taken on an empty stomach.
- Dosing will be based on body weight and CYP2D6 impairment status at the baseline visit, as shown in [Table 2](#).
- The starting dose is 6 mg in all patients. Daily doses will be administered twice daily, approximately 8 to 10 hours apart during the day. A minimum of 6 hours should elapse between doses. If a patient misses a dose and it is within 6 hours of their next dose, the missed dose should be skipped.
- After week 1, dose increases may not occur more frequently than every 5 days.
- Dose reductions, if required, should be in increments of 6 mg. **If more than 1 dose reduction is required for an adverse event, the medical monitor must be notified.**
- During the titration period, the dose of the IMP will be adjusted weekly according to [Table 2](#) to identify a dose level that optimally reduces tics and is well tolerated. Investigators will be blinded to CYP status, with a dose cap for poor metabolizers prespecified by the IRT.

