### 6.3. MISSING DATA

The handling of missing or incomplete data is described for each endpoint and data type (as needed) in Sections 8 to 9. In general, no data imputation will be applied for missing values in safety analysis. Data imputation method for efficacy analysis will be described in Section 8.

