## 7. DEMOGRAPHIC, OTHER BASELINE CHARACTERISTICS AND PRIOR MEDICATIONS

### 7.1. PATIENT DISPOSITION AND WITHDRAWALS

Patient screened and patients screened but not in the ITT analysis set will be summarized only for all patients in screened analysis set using patient counts. Patients in the ITT analysis set, patients in the ITT analysis set but not treated, patients in safety, mITT, and PP analysis sets, patients who complete titration period, complete maintenance period, complete the study, completed the follow-up, and patients who withdraw from the study (and reason for withdrawing) during each treatment period will be summarized using descriptive statistics. The ITT analysis set will be used as the denominator for calculating percentages.

If more than 15% of the patients withdraw from the study before the end of the treatment period, the number of days until study discontinuation will be analyzed using Kaplan-Meier methodology using the ITT analysis set (defined in Section 5.3). Patients who complete the study treatment period will be censored on the study day of the last dose.

A listing of study completion will be provided for all screened patients. A listing for analysis dataset with reason patient is excluded from the analysis set will also be provided for all patients in ITT analysis set.

In addition, the major protocol deviations will be summarized for ITT analysis set.

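### SAP 9.1 plans a Kaplan-Meier curve of time to the maximal dose without defining that dose or saying how patients who stop study drug below it are counted

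*SAP*

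**What the plan says.** SAP 9.1 (Extent of Exposure) plans three displays of dose attainment. The first is a count: "the frequency and percentage of patients reached the maximum daily dose allowed will be provided". The second is a bar plot of the same thing. The third is the curve: "A Kaplan-Meier Curve will be used to present the time to the maximal dose in days by treatment", with further splits by age group, weight group and CYP2D6 status. The count refers to the maximum daily dose allowed, the curve only to the maximal dose. Nothing in the section says who is censored, or when.

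The surrounding text does not fill the gap:

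- The denominator of the percentage follows from the general rule in SAP 9: "The safety analysis set will be used for all safety analyses".
- SAP 6.3 says only this about missing safety data: "In general, no data imputation will be applied for missing values in safety analysis".
- SAP 7.1 has a censoring rule, "Patients who complete the study treatment period will be censored on the study day of the last dose", but for a different curve, time to study discontinuation. That curve is produced only on a condition: "If more than 15% of the patients withdraw from the study before the end of the treatment period".

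Stopping below the cap can happen. Protocol 3.11 says: "A patient may discontinue participation in the study at any time for any reason".

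**The concern.** Once a patient has permanently stopped study drug, reaching the maximum dose is no longer possible. Stopping is therefore a competing event, whereas Kaplan-Meier has only events and censoring. Censoring a stopper at last dose treats that patient as someone who might still have reached the cap, and passes the patient's weight to those who stayed on drug. The curve then answers a hypothetical question (what if nobody stopped?), while the percentage beside it answers the factual one (how many treated patients got there?).

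The titration schedule makes this relevant here. In Protocol Table 2 and SAP Table 1, patients who are not CYP2D6-impaired first meet their cap (30, 42 or 48 mg by weight) in the Day 43-49 row. Apart from small shifts from the ±3-day visit windows, any of them who stops in the first six weeks leaves before the event could occur. Impaired patients can meet their cap from Day 15, 22 or 29, so the size of the effect can differ between the very groups the curve sets side by side.

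What is at stake is a clear reading of one exposure figure in a trial whose secondary objective includes the safety and tolerability of titration. As written, two programmers could draw different curves from the same data.

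**Working it through.** SAP 9.1 states no figure to reproduce, so the check compares the curve's end point with the plain percentage under explicit rules.

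**Inputs from the documents.** N = 58 per arm (SAP 3.5). The cap is first available to non-impaired patients on Day 43 (Protocol Table 2). On the last chance to raise a dose, Protocol 5.1 says: "Although dose adjustments can be made up to and including the week 7 telephone call". Week 7 is Day 49 and a new dose starts the next morning, so attainment is placed on Days 43 to 50. Treatment ends at Day 84.

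**Assumed, because the documents give neither.** Stopping rates of 5% to 20% (s = 3, 6, 9 or 12 of 58), and a share p of the patients who do not stop who reach the cap. The main case is p = 0.5, with 0.3 to 0.8 as the range. Let r be the number who reach the cap.

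**Stops all before Day 43, censored at last dose.** Only N − s patients are at risk when events begin, and nobody is censored while they occur, so

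- 1 − KM = r / (N − s)
- plain percentage = r / N
- gap = [r / (N − s)] × (s / N)

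| Stops | r | 1 − KM | Plain % | Gap (points) |
|---|---|---|---|---|
| 3 (5%) | 28 | 28/55 = 50.9% | 28/58 = 48.3% | 2.6 |
| 6 (10%) | 26 | 26/52 = 50.0% | 26/58 = 44.8% | 5.2 |
| 9 (15%) | 24 | 24/49 = 49.0% | 24/58 = 41.4% | 7.6 |
| 12 (20%) | 23 | 23/46 = 50.0% | 23/58 = 39.7% | 10.3 |

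With p from 0.3 to 0.8, the gap runs from 1.5 points (5% stopping: 16/55 against 16/58) to 16.6 points (20% stopping: 37/46 against 37/58).

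**Stops evenly spaced over Days 7 to 84, censored at last dose, p = 0.5.** With 3 stops (Days 7, 46 and 84) and 28 events, 57 patients are at risk at Day 43. Sixteen events by Day 46 leave 41/57. One more patient is then censored, and 12 further events take 40 at risk down to 28. So 1 − KM = 1 − (41/57) × (28/40) = 49.6%, against 48.3%. In full (gaps from unrounded values):

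| Stops | 1 − KM | Plain % | Gap (points) |
|---|---|---|---|
| 3 | 49.6% | 48.3% | 1.4 |
| 6 | 47.3% | 44.8% | 2.4 |
| 9 | 45.0% | 41.4% | 3.6 |
| 12 | 44.4% | 39.7% | 4.7 |

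**Cases with no gap.** If 9 patients stop, all after Day 50, and 25 reach the cap, both figures are 25/58 = 43.1%. If stoppers are instead kept in the risk set as not having reached the cap to Day 84, the curve ends at r/N: 26/58 = 44.8% with 6 early stops and 24/58 = 41.4% with 9. A cumulative incidence curve with stopping as the competing event ends at the same values.

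**The case against.** The strongest reply is that the defect is not on the page. SAP 9.1 gives no censoring rule, and the programming section, figure index and appendices are blacked out in the public copy, so a rule may exist there. A reader might infer that the plan does censor stoppers and that figure and table must disagree. The documents do not support that: if stoppers stay at risk to Day 84, the disagreement disappears. This part of the reply stands, and the point is therefore conditional.

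The event is also open to two readings. If the maximal dose means each patient's own highest dose, every dosed patient has the event and nobody is censored. The two preceding displays make the allowed maximum the more natural reading, but the text does not settle it.

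A reader might further infer that an inflated curve makes titration look better tolerated. It does not follow. Protocol 3.1.3 ends escalation on a sustained TS-CGI reduction as well as on a clinically significant adverse event, so a patient may stay below the cap because the drug is working. Patients who continue on a lower dose also remain in the risk set and do not inflate the curve.

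Nor should the 15% in SAP 7.1 be placed wholly in titration. It counts withdrawals over the whole treatment period. Spread evenly over 84 days, half (42/84) would fall before Day 43, and 0.5 × 7.5% is about 3.8 points, close to the 3.6 computed above for 9 spread stops.

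Finally, the plain percentage is already reported, withdrawals are tabulated by period, and the gaps for spread stops are below one arm's standard error, √(0.5 × 0.5/58) = 6.6 points. All true, and it limits the importance. It does not remove the point, because figure and table use the same patients, so a difference between them would come from the method and not from sampling.

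**Conclusion.** The point holds as a conditional and minor one. SAP 9.1 leaves undefined both the event and the handling of patients who stop below it. Under the usual default of censoring at last dose, the curve estimates a hypothetical share that lies at or above the reported percentage. For 58 per arm, with half of the patients who do not stop reaching the cap, the excess is about 1.4 to 4.7 points when 5% to 20% stop evenly over Days 7 to 84. It is 2.6 to 10.3 points when they all stop before Day 43. It is zero when stops come after the last patient has reached the cap or when stoppers are kept at risk to Day 84. The stopping rate, its timing and the share reaching the cap are assumptions.

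The display is descriptive and carries no test. Efficacy conclusions, type I error and power are unaffected.

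**What to change.** In SAP 9.1, define the event as the first day on which the patient takes the maximum daily dose allowed for his or her weight and CYP2D6 status. Replace the Kaplan-Meier curve with a cumulative incidence (Aalen-Johansen) curve in which permanent discontinuation of study drug before that day is the competing event. Patients who stay on a lower dose are followed to their last dose as not having reached it. A temporary suspension of the kind described in Protocol 5.5 is not the competing event. With complete follow-up, the curve's end point then equals the tabulated percentage.

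The cost is one sentence in the SAP and one option in the procedure that draws the figure. Dose start and stop dates are already collected on the CRF (SAP 6.2.2 and 9.2), so no new data or change in conduct is needed. The displayed share may come out slightly lower than a Kaplan-Meier curve would show.

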### 9.2. TREATMENT COMPLIANCE

Study drug administration will be included in the CRF. In the form, med ID (ID for blister pack), week range, dosing start and stop date, and number of pills taken from the blister pack are collected. Treatment compliance (%) is calculated as  $100 * (\text{total number of pills taken} / \text{number of tablets expected to be used})$ . The total number of pills taken is the sum of pills taken from all bottles dispensed, identified by med ID. If a patient does not return a pill bottle, it will be assumed that the patient took no study drug from that bottle for the purposes of calculating compliance. The number of pills expected to be used is based on the number of morning and evening dosing times

during the treatment period (2 pills are used for each dosing time point). A patient will be deemed compliant over the treatment period if the patient has taken 80% to 105% of the expected tablets of study drug.

Treatment compliance (%) will be summarized as continuous data using descriptive statistics. In addition, treatment compliance will be summarized as categorical data using descriptive statistics for the following categories: <80%, 80% to 105%, >105%.

### **9.3. CONCOMITANT MEDICATION**

A concomitant medication is 1) any medication that starts prior to first day of study drug administration and continues into treatment period; or 2) any medication that starts on or after the first dose of IMP and before the last dose of IMP. Concomitant medication will be summarized separately for 1) and 2). In the case of completely missing stop date and medication is not ongoing, medication will be assumed to be concomitant. Medication cannot be considered as both prior and concomitant.

Concomitant medication summaries based on ATC level 3 and the preferred drug names will be produced for the safety analysis set. The summaries will present, by treatment group, the frequency and percentage of patients who used any medication in an ATC class, or any medication based on a single preferred drug name. Medication summaries will be sorted by descending total frequency of ATC class and by PT within ATC class. Patients will be counted only once for each medication class and each preferred drug name.

In addition, ADHD and antidepressant (see Section [7.4.1](#) for ATC code list) change will be summarized for:

- Proportion of patients requiring new medication;
- Proportion of patients with requiring increased medication;
- Proportion of patients requiring decreased medication;
- Proportion of patients with medication switch.

### **9.4. ADVERSE EVENTS**

Adverse events will be collected and recorded from the time a patient signs the informed consent to the end of follow-up period. For this study, the follow-up period for recording of adverse events is defined as 1 week of washout for patients who will participate in the open-label safety extension study TV50717-CNS-30047 and 2 weeks after the last dose of IMP for patients who will not roll over into Study TV50717-CNS-30047.

For all AEs, preferred AE terms and system organ class (SOC) will be coded using terminology from the Medical Dictionary for Regulatory Activities (MedDRA), version 20.1 or higher.

A treatment emergent adverse event (TEAE) is defined as an AE that begins after the first administration of study medication or existing AEs that worsen after the first dose of study medication. All reported AEs will be listed, but only TEAEs will be summarized in tables.

Drug related AEs will be considered those to be reasonable possibility based on the investigators assessment. Missing relationship will be considered as “Related”.

Unless otherwise specified, AEs will be summarized by SOC and PT, with SOCs and PTs within SOCs presented in descending order of patient incidence.

AE summary tables are listed below:

- An overall summary of the number and percentage of patients reporting any TEAEs, serious TEAEs, treatment-related TEAEs, serious treatment-related TEAE, any TEAEs leading to study drug discontinuation, any TEAEs leading to patient study drug interruption, and TEAEs leading to death. The overall summary will also be prepared by age group (6-11 years, or 12-16 years);
- TEAEs overall and by SOC and PT;
- TEAEs by severity, overall and by SOC and PT. Missing severity, if any, will be assumed as “severe”;
- Serious TEAEs, overall and by SOC and PT;
- Serious treatment related TEAEs, overall and by SOC and PT
- TEAEs by relationship to study treatment, overall and by SOC and PT;
- TEAEs leading to study drug discontinuation, overall and by SOC and PT;
- TEAEs leading to study drug interruption, overall and by SOC and PT;
- TEAEs leading to dose reduction overall and by SOC and PT;
- Most common TEAEs, overall and by PT. Most common TEAEs are defined as TEAEs that occur in > 4% of the patients in either of the treatment groups;
- SMQs for suicide/self-injury, depression (exclude suicide and self-injury), and Parkinson-like events.

For summary tables, patients having more than 1 event with the same PT will be counted once for that term. Patients having more than 1 event with the same SOC will be counted once for each event and once for that SOC. For tabulations by severity, only a patient’s most severe event within the category (e.g. overall, SOC, PT) will be counted; similarly, for tabulations by relationship, only a patient’s most related event within a category will be counted. Summaries will be presented by treatment group and for all patients. The denominator for percentages will be the number of patients in safety analysis set for the given treatment group (i.e., the N’s for the columns).

Summary of all TEAEs will be presented in the overall period (titration plus maintenance phase

plus follow-up period) and for the titration period, maintenance period, and follow-up period. By period summary will be based on the period the AE occurred (Section 6.4). Same type of AE may be counted in multiple periods in cases below:

- AE resolved in the same period and reoccurred in a new period.
- AE increased severity in another period.

Same AE will be counted only once in summary in the overall period.

All adverse events in the overall treatment period will be summarized by CYP2D6 impairment status (Impaired/Not impaired). In addition, serious AEs and AEs by severity will be summarized by CYP2D6 impairment status.

Listings will be provided for all AEs and the following subsets:

- All AEs
- Serious AEs
- AEs leading to study drug discontinuation
- AE leading to dose interruption
- AEs leading to death.

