3.1.5. Washout Period and Follow-up

[figure not shown]
All patients will discontinue IMP at the week 12 visit and will return 1 week later for evaluation of safety and tic reduction (week 13). Patients who complete the study may be eligible to begin participation in the open-label safety extension study TV50717-CNS-30047. For this study, the follow-up period is defined as 1 week of washout for patients who will participate in the open-label safety extension study TV50717-CNS-30047 and 2 weeks after the last dose of IMP (1 week after the end of the washout period) for patients who will not roll over into the open-label safety extension study TV50717-CNS-30047. At the week 13 visit, patients may choose to enter Study TV50717-CNS-30047 (on that day), or they will have an additional week to make a decision and return for day 1. Patients not participating in Study TV50717-CNS-30047 will have a follow-up telephone contact to evaluate safety 1 week after the end of the washout period (2 weeks after their last dose of IMP).

Prohibited drugs will remain the same during the washout period for patients who will participate in the open-label extension study TV50717-CNS-30047.

Patients who will not participate in the extension study (Study TV50717-CNS-30047) may begin/resume tic therapy medication after the first week of the washout period.

See [Table 1](#) for study procedures and assessments.

See [Figure 1](#) for study schema.

Figure 1: Overall Study Schema

^a Maximum total daily dose for patients ≥40 kg is 48 mg/day (24 mg bid), 30 to <40 kg is 42 mg/day (21 mg bid), and 20 to <30 kg is 30 mg/day (15 mg bid). For those considered CYP2D6 impaired, maximum daily dose for patients ≥40 kg is 36 mg/day, 30 to <40 kg is 24 mg/day, and 20 to <30 kg is 18 mg/day (Table 2).

^b If a stable dose is reached before the indicated time, the patient should continue taking that dose for the remainder of the titration period and throughout the maintenance therapy dosing.

^c This is a telephone contact for safety evaluation, required only for patients who will not roll over into the open-label safety extension study TV50717-CNS-30047.

bid=twice a day; CYP=cytochrome P450; ET=early termination visit.

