Promethazine-containing compounds	Ziprasidone
Fluphenazine	Tiapride

Note: This table does not apply in the second week of washout for patients not rolling over to the open-label extension study (Study TV50717-CNS-30047).

Table 8: Other Prohibited Drugs

Generic	Class/clinical use	Note
Cannabidiol oil	Cannabis	Also includes other forms of cannabinoids
Valbenazine	Vesicular monoamine transporter 2 inhibitor	Ingrezza off-label
Quinidine	Class I antiarrhythmic agent	Strong CYP2D6 inhibitor
Terbinafine	Antifungal medication	Weak CYP2D6 inhibitor

APPENDIX B. DISTRIBUTION OF AUC BY WEIGHT CATEGORIES AND CYP2D6 STATUS**Figure 2: Distribution of AUC of Total ($\alpha+\beta$)-HTBZ for Selected Doses Based on Weight Categories**AUC=area under the curve; CYP2D6=cytochrome P450 2D6; α/β -HTBZ=alpha/beta-dihydrotetrabenazine.

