### 6.4. VISIT WINDOWS

After mapping the data to the analysis visits of unscheduled and early termination visits, the following rules will apply unless other handling is specified for a particular analysis.

- If there is scheduled visit in the analysis window, scheduled visit will be selected.
- If there is no scheduled visit, but early termination visit, early termination visit will be selected.
- If there are no scheduled or early termination visits, the unscheduled visit will be selected. If there are multiple unscheduled visits, the following rules will be used in sequential order:
  - The record closest to the planned assessment day will be selected for analysis.
  - If there are no scheduled or early termination visits, and 2 records are equidistant from the scheduled day, then the later record will be selected.
- If a patient has no scheduled record or early termination/unscheduled visits in an analysis window, the patient will be considered missing at that visit.

For these analyses performed by time period, e.g. adverse events, the following definitions will be used:

- Titration Period - from the first dose of treatment until the day before the week 7 telephone contact. For patients discontinued before the week 7 telephone contact, the Titration Period is until the later of the last dose of treatment and the early termination visit.

- Maintenance Period - from the day of the week 7 telephone contact until the day of the week 12 visit. If a patient enters the Maintenance Period but discontinues treatment early, the Maintenance Period is until the later of the last dose of treatment and the early termination visit.
- Follow-up Period - from the end of the Maintenance Period through the end of the study.
- Overall Period - includes the Escalation Period, the Maintenance Periods, and the Follow-up Period, if applicable.

If the AE onset date is partial and can be potentially counted in multiple periods, AE will be included with the earliest period.

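### Follow-up TEAE percentages depend on roll-over: 7 off-drug days are recorded for extension patients and 14 for the others, the second week open to new tic drugs, with no common cut-off

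*SAP*

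**What the plan says.** **Recording window.** SAP 9.4 (and Protocol 7.1.2) sets two lengths. For extension patients, "the follow-up period for recording of adverse events is defined as 1 week of washout for patients who will participate"; for the rest it is "2 weeks after the last dose of IMP for patients who will not roll over into Study TV50717-CNS-30047". The schedule agrees: IMP stops at week 12 (Day 84), all completers return at week 13 (Day 91), and the week 14 telephone contact (Day 98) is only for patients who do not roll over. Early discontinuers are also contacted two weeks after their last dose (Protocol 3.13.4).

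**Definition and tables.** SAP 9.4 states: "A treatment emergent adverse event (TEAE) is defined as an AE that begins after the first administration of study medication", or an existing event that worsens after it. No end is given. SAP 6.4 runs the Follow-up Period "from the end of the Maintenance Period through the end of the study". SAP 9.4 tabulates TEAEs for titration, maintenance and follow-up separately and for the three combined. Percentages use all safety patients in the arm as denominator, without person-time.

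**Medication in the second off-drug week.** Under Protocol 3.1.5, patients not entering the extension "may begin/resume tic therapy medication after the first week of the washout period". The note to Table 7 (prohibited antipsychotics) in Appendix A says: "This table does not apply in the second week of washout for patients not rolling over to the open-label extension study". Apart from drugs continued from before first dose, SAP 9.3 treats as concomitant "any medication that starts on or after the first dose of IMP and before the last dose of IMP".

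**The concern.** With no limit in the TEAE definition, the recording window is the only bound, and its length depends on whether the patient enters the extension. That choice follows randomization and may reflect how well the treatment worked or was tolerated. A fixed denominator does not adjust for it.

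The extra week also differs in kind. A patient who did not roll over may be taking a newly started antipsychotic, and an event it causes is counted as a TEAE of the randomized arm. The SAP 9.3 summary would not show that drug, so a reader of the tables could not see the reason.

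The Follow-up table is affected most. The overall table is affected less. The most-common TEAE table (above 4% in either arm) and the SMQ tables, including Parkinson-like events, are not said to be split by period, so they carry the same events. Safety and tolerability are the trial's secondary objective.

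**Working it through.** **Window lengths, from the schedule**

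- Extension patients: 91 − 84 = 7 days off drug.
- Other completers: 98 − 84 = 14 days off drug, a ratio of 2.
- First dose to end of recording: 91 against 98 days; 98/91 = 1.077, or 7.7% longer.

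This reproduces the one-week and two-week windows of SAP 9.4. They are nominal: visits have a 3-day window either side, and a roll-over patient who uses the extra decision week may be off drug for about 14 days with events formally recorded for one.

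**Effect on the Follow-up table**

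The documents give no roll-over share and no off-drug event rate, so both are assumptions. Take the same constant weekly rate h in both arms, so that there is no true difference, and let r be the share rolling over.

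- 7-day risk: p7 = 1 − exp(−h)
- 14-day risk: p14 = 1 − exp(−2h)
- Arm percentage: r·p7 + (1 − r)·p14
- Gap between arms: (difference in r) × (p14 − p7)

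At h = 0.05, p7 = 4.88% and p14 = 9.52%.

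- r = 0.85: 0.85 × 4.88 + 0.15 × 9.52 = 5.57%
- r = 0.65: 0.65 × 4.88 + 0.35 × 9.52 = 6.50%
- Gap 0.93 points, ratio 1.17; 0.0093 × 58 = 0.54 patient.

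| h per week | p14 − p7 (points) | Gap, 85% vs 65% | Patients in 58 | Gap, 80% vs 70% | Patients in 58 |
|---|---|---|---|---|---|
| 0.02 | 1.94 | 0.39 | 0.2 | 0.19 | 0.1 |
| 0.05 | 4.64 | 0.93 | 0.5 | 0.46 | 0.3 |
| 0.10 | 8.61 | 1.72 | 1.0 | 0.86 | 0.5 |

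With equal roll-over the gap is zero at any h, although the level in each arm still depends on r.

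**If new tic drugs double the second-week rate (assumption).** The 14-day risk at h = 0.05 becomes 1 − exp(−0.15) = 13.93%. The 85%/65% gap is 0.20 × (13.93 − 4.88) = 1.81 points, or about 1 patient in 58.

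**Effect on the overall table.** If a share b of each arm already has an on-treatment TEAE, the gap shrinks by the factor (1 − b). With b = 50% (assumption), 0.93 becomes 0.46 points, about 0.3 patient.

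**Sparse tables.** With 58 per arm, the 4% rule is met by 3 patients (3/58 = 5.2%) but not by 2 (2/58 = 3.4%). One late event can move a preferred term across the line.

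**With a common 7-day limit.** Both arms show p7 = 4.88% whatever r is, so the gap is zero among patients who complete treatment.

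**The case against.** The strongest reply is that the plan already isolates most of this. Titration and maintenance tables do not depend on roll-over, the affected events sit in a labelled follow-up table, and the tables are descriptive. In the cases computed, the gap is at most about one patient per arm. That stands, and it limits the weight of the point.

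Data are not lost either. Medications are recorded on the CRF through follow-up (Protocol 5.3), the week 14 contact reviews them, and all AEs are listed. Relatedness guidance (Protocol 7.1.4) lets an investigator attribute an event to other therapy, and SAP 9.4 tabulates TEAEs by relationship. The indexes of tables and listings are blank in the public copy, so one cannot say that no post-treatment medication listing is planned. All this stands, but a listing does not correct a percentage.

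Three stronger readings are tempting and not supported:

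- **That placebo events caused by new antipsychotics would mask a drug signal.** This needs such events to occur within about a week and more often on placebo. The documents give neither frequency nor direction, and distortion can run either way.
- **That every tic drug is permitted in the second week.** Appendix A attaches the exemption to Table 7 only; Table 8, which includes valbenazine and cannabidiol, has no such note.
- **That a 7-day limit also removes inequality from early stopping.** A patient stopping on Day 28 is recorded to Day 42, 49 days short of a roll-over completer at Day 91. With the limit it is Day 35, 56 days short.

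A further fair objection is that a 7-day limit on every table would take late deaths, serious events and suicidality events out of the main safety display of a paediatric trial. The fix below avoids this.

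**Conclusion.** The point holds as a modest defect in definition. Off-drug observation is nominally 7 or 14 days according to a post-randomization choice, the second week may include new tic drugs that the concomitant-medication summary omits, and nothing in the unredacted SAP truncates, stratifies or adjusts for it. The Follow-up table is directly affected; the overall, most-common and SMQ tables are affected slightly.

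A between-arm distortion requires roll-over, or use of new tic drugs, to differ by arm, which the documents do not quantify. Under 85% against 65% roll-over and 5% per week it is about 0.9 points, half a patient in 58, in either direction. A reader might infer that the trial's safety comparison as a whole is biased; the documents do not support that. The change is still worth making because it uses data already collected and needs no change to trial conduct.

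**What to change.** In SAP 6.4 and 9.4:

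1. Define the Follow-up Period table as events with onset through 7 days after the last IMP dose, for every patient.
2. Show events with onset on days 8-14 in a separate table or listing, with the number of patients observed that long as denominator, flagged for any tic medication started after the last dose.
3. Keep all serious events, deaths and suicidality events in the main tables through the end of recording.
4. Add, as a supplement, overall, most-common and Parkinson-like SMQ summaries limited to last dose plus 7 days.

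Unequal total observation from early stopping is a separate matter that would need period-specific or exposure-adjusted rates. Exposure adjustment alone would not remove the effect of drugs started in the second week, so it does not replace steps 1 and 2.

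The cost is one revised definition, a programming flag and a few more tables.
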